2.5 Summary Table of Objectives and Endpoints

Objectives	Endpoints	Timepoint(s) of evaluation of this endpoint (if applicable)
Primary Objective	As above	Maximum 12 weeks following enrolment
Secondary Objectives	As above	Maximum 12 weeks following enrolment

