MAIN STUDY PROCEDURES	 Randomisation 1 Multi-parametric MRI compared to biparametric MRI Randomisation 2 Targeted biopsy performed using image-fusion targeted and systematic biopsies compared to visual-registration targeted and systematic biopsies in patients with visible suspicious finding on either bpMRI or mpMRI. Duration of follow-up: For up to 12 weeks after enrolment.
OUTCOME MEASURES (PRIMARY ENDPOINTS)	
Randomisation 1	Proportion of clinically significant cancers, defined as any amount of Gleason >/=3+4 (ISUP Grade Group >/=2) on biopsy, detected in the randomised population of patients at risk.
Randomisation 2	Proportion of clinically significant cancers, defined as any amount of Gleason >/=3+4 (ISUP Grade Group >/=2) on biopsy, detected in the randomised population of patients biopsied for a suspicious MRI.
OUTCOME MEASURES (SECONDARY ENDPOINTS)	
	Proportion recommended for biopsy in randomised arm Proportion actually biopsied in each randomised arm

Proportion diagnosed with clinically insignificant prostate cancer (defined as any Gleason 3+3=6 [ISUP Grade Group 1])
Proportion of clinically significant and insignificant cancers using other histological definitions of clinical significance - PROMIS 1 and 2 - any Gleason >/=4+3 [ISUP Grade Group >/=3] - Gleason >/=3+4 [ISUP grade Group >/=2] or any Gleason 3+3 [ISUP Grade Group 1] of >/=6mm - Gleason >/=3+4 [ISUP grade Group >/=2] with >/=10% pattern 4 OR presence of cribriform pattern OR presence of intraductal components
Detection rates for each randomised group of known prognostic risk categories. These are D'Amico, National Comprehensive Cancer Network (NCCN) and Cambridge Prognostic Groups (CPG).
Adverse events and patient reported outcomes
Outcomes by centre stratified by size and type of MRI scanner, route of biopsy and amount of systematic sampling.
Healthcare resource utilisation, costs and cost- effectiveness of using fastMRI compared to mpMRI and image-fusion compared to cognitive targeted biopsies
Consent for linkage to national databases to collect medium and long-term outcomes including new diagnostic tests, prostate cancer diagnoses and treatments, deaths and prostate cancer deaths

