Since biopsies can cause side-effects such as pain, bleeding and infection, a non-suspicious mpMRI can allow some men to avoid an invasive biopsy as the probability of clinically significant prostate cancer is low. In the UK, a decision on whether to carry out a biopsy is then based on the mpMRI findings in combination with other clinical factors: about a guarter can avoid an immediate biopsy due to a low risk of harbouring clinically significant prostate cancer. In most centres, if a biopsy is indicated, it is guided by ultrasound with the operator estimating where to deploy the biopsy needle in order to take tissue samples; what is commonly referred to as visual-registration targeting. We want to test two major changes that might further improve this new pathway.

First, mpMRI takes 40 minutes, requires intravenous gadolinium contrast and costs £239 (NHS HRG 2020 Tariff) in the UK NHS. Administration of gadolinium requires medical supervision due to a risk of anaphylaxis. Further, there is concern about its deposition in the brain although there is uncertainty about whether this causes harm. In addition, many hospitals struggle with scanner time and this can lead to patients with suspected prostate

cancer and other medical conditions waiting longer [Royal of College of Radiology 2017]. A 15 minute, bpMRI that does not involve injection of gadolinium contrast and costs £141 (NHS HRG 2020 Tariff) might be as accurate as mpMRI in ruling-out and detecting clinically significant prostate cancer.

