Further, capacity constraints mean that many hospitals are unable to scan all the men referred with suspected prostate cancer quickly enough to meet NHS cancer waiting time targets. Indeed, the extra prostate mpMRI scans might lead to patients with other medical conditions having to wait longer. An April 2017 Royal College of Radiology report stated that of 53 organisations surveyed, the mean anticipated increase in workload for scanning was 13%. This survey was conducted prior to the PROMIS study was published and might be an underestimate as it did not take into account the number of expected prostate mpMRI scans. A bpMRI would free up over 4,500 days of scanner time every year within the NHS, equivalent to approximately 100,000 extra bpMRI scans per year. This is because examination time for scanning is different to MRI time slots which have to include the time taken to safety-check, set-up intravenous access and set up the contrast pump, get patients into the magnet/positioned, perform planning sequences, localisers, and after scanning getting the patient off the table. The immediate cost saving to NHS commissioners in tariff payments of not having to use contrast-enhanced mpMRI would be £6.7 Million every year, with further potential savings from not requiring on-site medical cover and reductions in the length of time to review scans as there are fewer images to look at, so helping to free up expert radiology time. The NHS will also be able to scan more patients in a timely fashion.

Second, for those men needing a targeted biopsy, visual-registration requires highly skilled operators that are not available everywhere. This means that clinically significant cancers might be missed. Image-fusion technology that overlays MRI and ultrasound images might improve the detection of clinically significant prostate cancer as they can guide the biopsy needle to within 2-3mm accuracy.

Figure 2. MRI to ultrasound image fusion for targeted biopsy. The lesion is not visible on ultrasound so visual-registration targeting would be based on the operator looking at the MR-images on a separate screen (which is often in a different room) and then estimating where to deploy the needles. With image-fusion, tissue deformation and rotation can be taken into account with the lesion demonstrated as an overlaid contour on the ultrasound.

bpMRI and mpMRI

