For each randomisation, the number and proportion of clinically significant cancers detected in the randomised population will be reported by trial arm. Group differences will be quantified by the risk difference with two-sided confidence intervals at a level appropriate to the significance level pre-specified in the sample size. Detection rates will be compared by trial arm using mixed models with adjustment for trial arm allocation of co-enrolled trial and random effect by centre. The treatment effect coefficients will be presented with confidence intervals and associated p-value. The primary analysis will be conducted on an intention-totreat (ITT) basis, where patients with missing outcomes are assumed not to have clinically significant prostate cancer. A modified ITT analysis will be performed excluding patients who did not complete the diagnostic tests, and for the non-inferiority comparison a per protocol analysis including only those undergoing randomly assigned interventions. A pre-specified statistical analysis plan will be drafted detailing intended analyses for primary and secondary outcomes. It will be approved by the IDMC and agreed prior to analysis.

Cost-effectiveness analysis

A within trial cost-effectiveness analyses will estimate the incremental cost per true positive detected and incremental cost per correct diagnosis. Estimates of diagnostic performance will be based on the trial analysis and costs will be estimated from the NHS and PSS perspective using a micro-costing approach for tests. Deterministic (to explore plausible alternatives e.g., quantity of resources used or unit costs) will be combined with stochastic

IP7-PACIFIC Protocol No: 22CX7488	Imperial College London	V3.0 18 th December 2023
-----------------------------------	-------------------------	-------------------------------------

sensitivity analysis (used to explore statistical imprecision in estimates of costs, effects and cost-effectiveness).

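### The primary endpoint is capped at 12 weeks from enrolment and missing results count as no cancer, so late biopsy results would pull the arms of randomisation 1 together and favour non-inferiority

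*Protocol*

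**What the plan says.** Section 2.5 gives the evaluation time point for the primary and the secondary objectives as "Maximum 12 weeks following enrolment". The Trial Summary describes follow-up in the same terms ("For up to 12 weeks after enrolment"), and Section 5.2 repeats the 12-week maximum. All three count from enrolment.

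Section 2.3 defines the randomisation 1 endpoint as the proportion with Gleason 3+4 or higher on biopsy in the randomised population, with no time limit.

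The visit table (Section 5.4) allows MRI in weeks 1-8, biopsy in the same weeks 1-8, and biopsy results in weeks 2-12. Its notes say that biopsy may be on the day of the MRI in some centres, and that biopsy outcomes come from the medical record.

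Section 8.3 makes ITT primary and states that "patients with missing outcomes are assumed not to have clinically significant prostate cancer". It also plans supporting analyses: "A modified ITT analysis will be performed excluding patients who did not complete the diagnostic tests", and a per-protocol analysis for the non-inferiority comparison.

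On capacity, Section 1 says that "many hospitals struggle with scanner time" and that "many hospitals are unable to scan all the men referred with suspected prostate cancer quickly enough to meet NHS cancer waiting time targets". It gives 40 minutes for mpMRI and 15 for bpMRI.

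**The concern.** The objective is to find significant cancer after one type of scan or the other, not to find it by a given week. Booking, scanning, reporting, biopsy and histology must all fit into 12 weeks that start before the scan is booked. Followed as written, a cancer reported in week 13 on a biopsy that the trial MRI prompted leaves the numerator, while the man stays in the denominator as a negative.

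In a superiority trial such losses would mostly cost power. In a non-inferiority trial they help the claim. If both arms lose the same fraction of detections, a true deficit shrinks in proportion. If mpMRI loses more, the observed deficit shrinks further, for a reason unrelated to diagnostic yield. Either way, the chance of recommending bpMRI when it truly loses 5 points exceeds the 5% that the design allows.

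**Working it through.** **Inputs from the protocol (Section 8.1 unless noted).** Detection 38% in both arms; margin 5 points; one-sided alpha 0.05; power 90%; 1615 per arm, 3230 in total; target 3600 with about 10% attrition; 55% and 65% detection among men biopsied for a suspicious MRI (randomisation 2).

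**Assumptions, because the protocol gives no delay data.** The fraction of detections lost to the cap, m, equal in both arms: 5% or 10%. The excess of mpMRI men with a late result, x: 1, 2 or 3 points. The yield among those late men: 38% (no different from all randomised men) to 60% (midpoint of 55% and 65%).

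**Step 1, the plan's own figure.** n per arm = (1.645 + 1.282)² × 2 × 0.38 × 0.62 / 0.05², rounded up, = 1615, or 3230 in total. This reproduces the stated size. Allowing 10% attrition, 3230/0.90 = 3589, against the stated 3600. The sample size is not in question.

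**Step 2, error rate at the margin.** Take true rates of 38% (mpMRI) and 33% (bpMRI). If the observed difference is shifted by s towards non-inferiority, the false non-inferiority rate is 1 − Φ(1.645 − s/SE), with SE = √[(p₁(1−p₁) + p₂(1−p₂))/1615] at the observed rates. With s = 0 this is 5%.

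**Step 3, equal loss in both arms.** Observed rates are 0.38(1−m) and 0.33(1−m), so s = 0.05m.

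| m | Observed mpMRI | Observed bpMRI | Difference | SE | False non-inferiority |
|---|---|---|---|---|---|
| 5% | 36.10% | 31.35% | −4.75 points | 1.66 points | 6.8% |
| 10% | 34.20% | 29.70% | −4.50 points | 1.64 points | 9.0% |

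**Step 4, extra loss on mpMRI only.** Here s = x × yield. At 38% yield the SE uses the reduced mpMRI rate (1.68 points in each row). At 60% yield it uses 38% and 33% (also 1.68 points).

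| x | s at 38% yield | False non-inferiority | s at 60% yield | False non-inferiority |
|---|---|---|---|---|
| 1 point | 0.38 points | 7.8% | 0.6 points | 9.9% |
| 2 points | 0.76 points | 11.7% | 1.2 points | 17.6% |
| 3 points | 1.14 points | 16.7% | 1.8 points | 28.3% |

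The protocol's own figures imply a yield of 0.38/0.70 = 54% among men recommended for biopsy, which lies inside this range. Using all 1800 randomised men per arm at 38% yield gives 8.0%, 12.2% and 17.7%, so the choice of denominator matters little.

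**Step 5, does the protocol keep to 12 weeks elsewhere?** Section 5 places the last questionnaires 35-90 days after biopsy. For a biopsy in week 8 (day 56) that is day 91 to day 146, or week 13 to about week 21. Section 2.5 nevertheless caps the secondary endpoints at 12 weeks (day 84) as well. Data collection past week 12 is thus already implied.

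**The case against.** **The rule is not written out.** No section says that a result after week 12 is missing. The time point sits in a summary table, Section 2.3 has no limit, and Section 5.2 treats database lock as the practical limit for treatment decisions. Handling of late results could be left to the statistical analysis plan. This stands in part: the reading combines Sections 2.5 and 8.3. But the protocol does fix a maximum for its primary endpoint, and that maximum conflicts with the untimed definition and with the questionnaire schedule.

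**Longer waits for mpMRI.** A reader might infer from Section 1 that men allocated to mpMRI will wait longer in this trial. The documents do not show that. Section 1 argues about throughput across the health service, Section 5 says both scans run on the same scanners, and Section 11.9 describes men often booked directly for MRI. No waits by arm are given, so an arm difference is a possibility only.

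**The visit table.** A reader might also infer that a man scanned in week 8 has no time left for a biopsy. The biopsy visit window does end at week 8, but results are accepted to week 12, so under the 12-week limit he has about four weeks.

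**Late results may be rare.** Consent for both randomisations is taken at the outset partly to help centres meet a 28-day diagnosis target, and 12 weeks is three times that. Section 8.3 allows three months for MRI, biopsy and histology together and monitors outcome completeness in the pilot. This bears on size, and it stands.

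**Supporting analyses.** The modified ITT and per-protocol analyses, and the planned reporting of biopsies advised and done, would help to reveal a problem. They do not remove it from the primary analysis. A man biopsied in week 13 did complete his tests and had his assigned scan, so he could stay in both supporting sets and still count as negative.

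**An open-ended endpoint would be no better.** Counting any biopsy before database lock would give early recruits a much longer look-back over the 30 months of recruitment in Section 8.2. This is right, and the fix below uses a fixed window.

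**Conclusion.** The concern holds as a conditional bias in how the primary endpoint is fixed. It is neither an arithmetic error nor a demonstrated imbalance between arms. If the 12-week maximum is applied together with the missing-outcome rule, the effect of late results is towards non-inferiority even when they are equally common in both arms: about 7% or 9% false non-inferiority instead of 5% for 5% or 10% of detections lost. The larger figures (8-10%, 12-18% and 17-28%) need an excess of late results after mpMRI of 1, 2 or 3 points, and a yield of 38-60% among those men. These are assumptions, and if nothing is lost to the cap, nothing changes. It would go too far to conclude that the trial is biased by slower mpMRI slots. What the documents support is that the primary endpoint should not depend on how quickly scans and biopsies are delivered.

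**What to change.** In Sections 2.3 and 2.5 and the Trial Summary, define the randomisation 1 primary endpoint as histology from the first biopsy episode recommended on the trial MRI, taken from the medical record within one fixed window, the same for all men and long enough to cover delayed biopsies. Set database lock after that window closes for the last man enrolled.

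- Choose the length before any comparison by arm, for instance from pilot times to biopsy pooled over arms. Keep it short of the 6-12 months at which Section 5 says some unbiopsied men are reviewed with a new PSA, so that later re-investigation is not counted.
- Attribute the biopsy to the trial MRI from the recommendation already recorded in the eCRF (Section 10.4), since only pathologists are stated to be blinded. Say whether a biopsy done by patient choice against advice counts.
- Report time from randomisation to MRI and to biopsy by arm.
- Keep detection within 12 weeks as a sensitivity analysis.

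The cost is protocol wording, one further record check for men with a biopsy recommended but no result at week 12, and possibly a slightly later lock. Visits, questionnaires, clinical management and the sample size are unchanged.

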3. STUDY DESIGN

IP7-PACIFIC incorporates two linked RCTs which will test whether bpMRI and image-fusion make a difference if used in clinical practice, across multiple centres, without the incorporation bias inherent in paired-cohort studies [Stabile et al, 2018]. Our design provides economies of scale and scope compared to addressing these research gaps with two separate RCTs.

Since bpMRI is an abbreviated examination, clinicians and patients require reassurance that it is no worse than mpMRI. Therefore, we plan a non-inferiority evaluation. The second randomisation will involve co-enrolment of a subgroup of the first randomised group i.e., patients referred for biopsy following a positive MRI result. To justify the extra cost for the technology, we would expect image-fusion to detect more clinically significant cancers than visual-registration targeting.

3.1 Design

4. PARTICIPANT ENTRY

4.1 Study setting and population

Patients referred to hospital urology departments by their GP due to a clinical suspicion of prostate cancer (elevated serum prostate specific antigen [PSA], abnormal feeling prostate on rectal examination, or both). These patients are normally recommended to undergo a prostate MRI as part of standard care.

Randomisation-1: bpMRI versus mpMRI

Patient population

Inclusion criteria

- Age 18 years or above (no upper limit)

- Patients with a prostate (either cis-male gender or trans-female gender with no prior androgen deprivation hormone use at all).

- Referred to hospital and advised to undergo a prostate MRI because of an abnormal digital rectal examination (regardless of PSA level) and/or an elevated PSA (within 6 months of screening visit)

PSA >/=3.0ng/ml for age 50-69 years PSA >/=5.0ng/ml for age >/=70 years If family or ethnic risk for prostate cancer, PSA >/=2.5ng/ml for age 45-49 years

Explanatory note: Patients with elevated age-specific PSA or abnormal digital rectal examination of the prostate (or both) with PSA levels as determined by NICE guidance and local NHS Cancer Alliance or regional guidance. Recent UK consensus guidance [Prostate Cancer UK, 2016] from over 300 UK healthcare professionals and patients affected by prostate cancer and endorsed by the British Association of Urological Nurses (BAUN), the British Association of Urological Surgeons (BAUS) and the Primary Care Urology Society (PCUS) also stipulates that patients with a family history (1 or more first degree male relatives) or ethnic risk group (those identifying as of Black-African/Black-Caribbean) should be further investigated with PSA >/=2.5 when aged 45-49 years. We will also approach these patients if they are referred by their GP to secondary care. No upper age limit will be set.

Exclusion criteria

- PSA >50ng/ml. The rationale being that above this PSA level, rates of clinically significant prostate cancer are quite high.
- Prostate MRI or prostate biopsy within the previous 24 months from the date of screening. A prior prostate MRI which is negative will add selection bias and change prior probabilities of disease whilst a prior biopsy can cause artefact changes which affect the quality of the images. These artefact changes can take a number of months to dissipate and in some patients up to 12-18 months after the biopsy.
- Prior prostate cancer diagnosis at any time-point. Patients on active surveillance will have differing prior probabilities of clinically significant prostate cancer to those referred with a clinical suspicion and are therefore excluded.
- Any absolute contraindication to MRI, gadolinium or biopsy. Patients with bilateral hip prostheses are excluded. These prostheses often cast a large imaging artefact over the prostate area on MRI and radiologists prefer a mpMRI scan because the diffusion images

can be particularly affected. In other words, there is lack of equipoise in these patients for randomisation between mpMRI and bpMRI.

- Contraindication to performing a biopsy guided by a transrectal ultrasound probe
- Unable to give informed consent to the study

Randomisation-2: Visual-registration targeting versus image-fusion targeting

Inclusion

Suspicious finding on mpMRI or bpMRI from randomisation-1 requiring targeted biopsy (MRI categories 3, 4 or 5)

Exclusion

As above for randomisation 1 Patient refusal for biopsy

5. PROCEDURES AND MEASUREMENTS

Randomisation 1: bpMRI versus mpMRI

Biparametric MRI (bpMRI) of the prostate followed by prostate biopsy in those with an ongoing clinical suspicion compared to multi-parametric MRI (mpMRI) of the prostate followed by prostate biopsy in those with an ongoing clinical suspicion. Sites and clinicians will be assessed for quality of conduct and reporting of MRI and biopsy. Standardisation and training meetings will be held of radiologists (to ensure consistency of reporting) and biopsy operators (to ensure a uniform high quality approach to biopsy). Radiologists will issue both a PIRADS [latest version as defined in MRI Reporting SOP] and Likert score.

Both bpMRI and mpMRI can be carried out on the same NHS scanners. A study-specific imaging protocol will set out the criteria that all centres will have to comply with, which will be in line with UK and international guidelines with images and radiologists undergoing quality control. bpMRI will comprise multiplanar T2-weighted and axial diffusion-weighted components whereas mpMRI will have these combined with gadolinium contrast-medium enhancement. Minor imaging protocol differences between scanners are often necessary to optimise individual MRI devices and this optimisation will be undertaken as described below, if necessary. Most centres have already started such quality control programmes as a result of work that some of our group ([name], [name], [name]) have contributed to through Prostate Cancer UK and NHS England.

Quality control (MRI/reporting)

Radiology expertise: We will include a number of centres with a range of patient volumes. NHS Cancer Alliances have been engaged in a standardisation programme since 2017 for prostate MRI conduct and reporting and our proposal will involve additional training and standardisation meetings before and straight after the pilot to incorporate any learning from the pilot itself. Reporters will also need to have completed or be a Faculty member of the free PCUK/RCR-approved online course (https://www.raiqc.com/sign-in/) or equivalent British Society of Uro-radiology or European Society of Uro-radiology course. Further, we will adopt a recent UK certification consensus (of which [name] and [name] were members) so that only level 2 and 3 radiologists are asked to participate [Barrett et al, 2020]; level 1 are non-radiology specialists and junior radiologists neither of whom would be appropriate as reporters in current NHS practice and thus in this study [Westphalen et al, 2016].The certification process will broadly follow these principles:

- Questionnaire (similar to Table E1 of Westphalen et al, 2016) and also ask about biopsy operators/pathology experience and pathology compliance with WHO/ISUP (RCPath) standards.
- Submission of overall findings from 100 cases (both positive and negative) from biopsy-naïve patients to include data on experience, image quality (internally rated), scoring (Likert/PIRADS [latest version as defined in MRI Reporting SOP]) breakdown and distribution with biopsy outcome where done. This can be from an existing or completed audit, and can be overall summary metrics rather than a full anonymised submission of 100 cases.

In addition, bpMRI and mpMRI scans will be double reported to evaluate inter-observer variability as per the Statistical Analysis Plan.

Reporting scheme: NICE currently recommends the use of the Likert scoring system with data showing its equivalence to PIRADS scoring. Our systematic review showed that of 44 studies, 21 used Likert scoring and 14 used PIRADS scoring with the other studies not stating the scoring system they used. In the PIRADS and Likert scoring systems, contrastenhancement is used in interpreting equivocal lesions. Since neither PIRADS or Likert can be fully applied for bpMRI, and as there is current heterogeneity of MRI scoring practice and uncertainty around which scoring system to use, we propose that both PIRADS (as per latest version determined in the MRI SOP) and Likert should be used in bpMRI and mpMRI evaluations. Our UK clinician survey indicated that 40% use Likert scoring and 53% use PIRADS; all who agreed to take part in the study also agreed to report both scores in the study.

Decision for biopsy

Decision to recommend biopsy: The decision-making around which groups of patients to recommend a biopsy will be in concordance with NICE guidance 2019 and reflect the

IP7-PACIFIC Protocol No: 22CX7488	Imperial College London	V3.0 18 th December 2023
-----------------------------------	-------------------------	-------------------------------------

majority of our clinicians' view in our recent survey. We have wide clinical consensus that those patients with a suspicious MRI (score 4 and 5 on either Likert or PIRADS [latest version as defined in MRI Reporting SOP]) should be advised to undergo a biopsy. Patients with a non-suspicious (score 1, 2) or equivocal MRI (score 3) (on either Likert or PIRADS [latest version as defined in MRI Reporting SOP]) with one or more risk factors (PSA density >/=0.12ng/ml/ml or >/=0.15ng/ml/ml, family history or ethnic risk) may also be recommended to have a biopsy. Normal practice at each centre will be declared prior to study recruitment. We shall report the number of patients recommended for biopsy included in the analysis who had a non-suspicious bpMRI/mpMRI and of these, the numbers of clinically significant and clinically insignificant cancers subsequently detected. We shall also report the number of patients who were recommended to have a biopsy but chose not to have it.

Follow-up of patients not undergoing a biopsy: Patients will be discharged back to the GP by their clinical team after their MRI with individual advice about the level of PSA that should lead to a referral back to hospital. Sometimes the clinical team reviews a patient 6-12 months later with another PSA level. The NICE guidance have set out key parameters for follow-up within primary or secondary care for patients who do not have a biopsy or end up with a negative biopsy and this will be the approach we advise centres to take (see sections 1.2.10-1.2.13, 9th May 2019, NICE Guidance NG131 [4]). Some patients with significant lower urinary tract symptoms will need ongoing follow-up and care as well as any relevant procedures for benign prostatic hyperplasia. The trial protocol will not stipulate the type of follow-up that occurs after biopsy as this is beyond the remit of the current proposal. We will collect information on whether additional tests or procedures were carried out within the 3 months of trial follow-up using our patient questionnaire. Future long-term outcomes through national database linkage will be collected, however, only if funding for such research activity is successful.

Randomisation-2: Visual-registration targeting versus image-fusion targeting

Targeted biopsy with either commercially available CE-marked image-fusion devices or visual-registration. The study will pragmatically permit any CE-marked image fusion device depending on local availability. For centres that do not have image-fusion devices, we have incorporated costs for hiring these for centres. All patients will undergo non-targeted systematic </=12 core biopsies or transperineal sectoral biopsies as well. The type of systematic biopsy approach will need to be declared by each centre at the beginning of the study and reasons for deviations from the standard systematic biopsy approach will be collected.

Biopsy

Expertise: There are no guidelines on what level of biopsy experience is required by clinicians in the NHS nor whether there should be minimum annual numbers for being designated as competent in targeted biopsy. Therefore, a robust study-specific standardisation programme will be used for all clinicians carrying out biopsy. For those centres using certain biopsy image-fusion devices, company-specific training modules and competency sign-off will need to occur. Whilst a minimum number of targeted biopsies has not been recommended in any guideline, our clinical opinion from experienced biopsy operators is that a minimum of 100 cases should have been carried out using the technique being proposed. We will also record the experience of each biopsy operator in terms of number of biopsies (to the nearest 50), years of experience and the specialty of operator (radiology, urology, nursing).

IP7-PACIFIC Protocol No: 22CX7488	Imperial College London	V3.0 18 th December 2023
-----------------------------------	-------------------------	-------------------------------------

Targeting and systematic biopsy protocol: We will follow standard care for centres in terms of type of analgesia/anaesthesia. Our clinician survey shows centres are using local anaesthetic, sedation or general anaesthetic; transperineal or transrectal route and visual-registration or image-fusion targeting. The exact anaesthesia type (local only, sedation, general anaesthetic) will be recorded. Number of systematic cores will be as described above with 6 cores per target (divided into 4+2 for the first lesion only) and unlimited targets in total per patient [Hansen et al, 2020; Leyh-Bannurah et al, 2020; Kenigsberg et al, 2018]. Targeted biopsies will be carried out first, in order to minimise the impact of swelling on obtaining accurate sampling of targets.

Histology

The histological report will evaluate the following aspects for each target and each location of systematic biopsies carried out according to Royal College of Pathology (UK) guidance [Royal College of Pathology Guidelines, 2016]: number of biopsies, number positive for cancer, core length in mm, cancer presence, maximum cancer core length in mm (where continuous and discontinuous numbers are given, for the purpose of analysis, the continuous number will be used), primary, secondary and highest Gleason grade, percent pattern 4 and presence of cribriform pattern when Gleason 3+4, perineural invasion/lymphovascular invasion/intraductal components/neuroendocrine differentiation; and vii) other features (high grade prostatic intraepithelial neoplasia/atypical acini/inflammation/atrophy). See Biopsy Reporting SOP.

Definition of clinically significant prostate cancer on histology

We know that some prostate cancers are clinically significant, and that other prostate cancers are clinically insignificant. Whilst there is still some uncertainty about exactly what entails clinical significance, particularly with respect to whether patients diagnosed with low volume Gleason 3+3 or Gleason 3+4 cancer should be on active surveillance, most physicians, researchers and guideline panels agree detection of Gleason >/=3+4 (ISUP grade Group >/=2) is the key target condition for any screening or diagnostic pathway. As a result, this is the primary histological threshold we will measure.

There is also acknowledgement that a low amount of cancer or low percent pattern 4 is perhaps not as aggressive. So, whilst the primary outcome measure will be the detection of any Gleason >/=3+4, there are important secondary definitions of clinical significance that we will measure as well. These definitions will incorporate the wide and divergent views on clinical significance but incorporate evidence on the amount of pattern 4 and maximum cancer core length as being significant elements [26-30]. These definitions will be:

- any amount of Gleason 4+3=7 or more
- any amount of Gleason >/=4+3 OR Gleason 3+3=6 of >/=6mm (PROMIS definition 1)
- any amount of Gleason >/=3+4 OR Gleason 3+3=6 of >/=4mm (PROMIS definition 2)
- any amount of Gleason >/=3+4 OR Gleason 3+3=6 of >/=6mm (PROMIS definition 3)

- any amount of Gleason 3+4=7 with cribriform pattern or a ductal component or >/=10% pattern 4 or any Gleason >/=4+3 [van Leenders et al, 2020].

Further, we will use risk groups as defined by D'Amico, NCCN and CPG (using the latest versions that are published at the time of the Statistical Analysis Plan being finalised).

Validated patient reported outcome measures

The ProBE PETB questionnaire included: Hospital Anxiety and Depression Scale (HADS) score, and urinary, bowel, and sexual symptoms assessed by using the validated University of California, Los Angeles petb

state Cancer Index questionnaires. The UCLA-PCI questionnaires have now been converted into the Expanded Prostate Index Composite (EPIC).

- We will compose a modified questionnaire to incorporate the latest versions of EPIC into the ProBE questionnaire. So, the questionnaire in IP7-PACIFIC will incorporate the following: HADS, EPIC (Urinary, Erectile and Bowel domains) and the EuroQol (EQ-5D-5L) will be used in the study as a generic measure of health-related quality-of-life which can be linked to public preferences [Janssen et al, 2013].

- Patients will be asked to self-report pain and discomfort (referred to as pain hereafter) immediately after and seven days after biopsy on a 4-point Likert-type scale as none, mild, moderate, or severe. Specific related complications such as fever, flu-like shivers, pain, haematuria, haematochezia, and haemoejaculate will be self-reported at 7-14 days after biopsy (or after MRI if no biopsy carried out) and at 35 to 90 days after prostate biopsy as absent or present following biopsy on a purpose designed questionnaire. For each symptom, patients will be asked to score the degree of "problem" as none, minor, moderate, or major. This will be used to derive a binary outcome for each symptom (present/moderate/severe problem vs. absent /minor problem).

The timepoints for the questionnaires are also referenced in the Patient Reported Outcomes and Experience Questionnaire as follows:

- Hospital Anxiety and Depression Scale (HADS) score questionnaire
 - Time-points: After Consent, 7-14 days after biopsy (or after MRI if no biopsy) and 35-90 days after biopsy
- EPIC (urinary, erectile, bowel)
 - Time-points: After Consent, 7-14 days after biopsy (or after MRI if no biopsy) and 35-90 days after biopsy
- EuroQol (EQ-5D-5L)
 - Time-points: After Consent, 7-14 days after biopsy (or after MRI if no biopsy) and 35-90 days after biopsy
- Questionnaire on MRI related side-effects
 - To be given to all patients to be completed after the MRI but before the biopsy (if they have a biopsy)
 - Questionnaire on biopsy related side-effectsTo be given to all patients who have had a biopsy
 - Time-points: 7-14 days after biopsy and 35-90 days after biopsy

These can be completed on paper and uploaded to the eCRF or completed electronically. We will ask consent from patients to be contacted by the central study team in order to issue and collate these directly from the central trials team. Completeness of data and patient questionnaire response rates is an important outcome in IP7-PACIFIC as it informs our analysis of side-effects and adverse events. We will prompt patients to complete the questionnaires sent to them by text or email with up to two reminders; this will be coordinated CONFIDENTIAL Page 26 of 55

by the central trials team. The researchers at the participating centres may also co-ordinate with the departmental clinic appointments in order to hand the questionnaires to the patient personally.

